This project will develop and evaluate a training intervention that aims to improve outcomes from a strategy-based rehabilitation intervention, Goal Management Training (GMT), by adding process-based cognitive training with adaptive difficulty to enhance the executive function of working memory updating (WMU). People with ABI (n=32) will complete 9 sessions of GMT, a recommended treatment for deficits in frontal-lobe executive functions, with the addition of 8 WMU training sessions with or without adaptive training. Measures of feasibility, acceptability, and fidelity will be taken, and effect sizes of differences in pre- to post-training changes on neural, cognitive, and functional measurements will be determined by comparing two experimental groups in which difficulty of the WMU training tasks either adaptively increases in response to performance or is fixed.

1. Introduction

Globally, stroke and head injury are leading causes of disability. Deficits in cognitive functions are common in these conditions, including impairment in frontal-lobe 'executive' functions such as working memory and the ability to solve problems, plan, and regulate actions in order to achieve intended goals. These deficits affect individuals' ability to live independently, work, and maintain social relationships. We propose that improving outcomes for people with acquired brain injury (ABI) requires an interdisciplinary approach in which neuropsychological rehabilitation and cognitive neuroscience complement one another.

In neuropsychological rehabilitation, interventions are classified as 'restorative' (restoration of underlying core cognitive processes including executive functions) or 'compensatory' (compensation of function through the use of external aids or learned strategies). Clinical guidelines recommend the use of 'meta-cognitive strategy training' for the treatment of deficits in frontal-lobe executive functions (Cicerone et al. 2011). Goal Management Training (GMT) is one such validated meta-cognitive strategy. GMT trains compensatory mental **strategies** to manage attention during multi-step tasks. GMT has been evaluated behaviourally in randomised controlled trials with positive, albeit modest, outcomes in individuals with ABI (Tornås et al., 2016).

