The primary aim of the study is to investigate whether it is feasible and acceptable to deliver a novel intervention combining GMT with WMU training, within a randomised controlled trial (RCT) context in a sample of ABI individuals. A further aim is to examine the behavioural and neural changes related to the novel intervention as well as the effect sizes.

3. Research Question

This project will combine methods from neuropsychological rehabilitation and cognitive neuroscience to answer the following: 1) Is it feasible to combine an existing treatment for executive dysfunction, GMT, with an adaptive WMU training and how much benefit is gained? 2) Does the novel treatment combination promote neural plasticity that is detectable using fMRI?

i. Primary

Primary outcomes will be measures of feasibility, acceptability, and fidelity.

ii. Secondary

Secondary outcomes will be pre- to post-training change in behavioural data (i.e., neuropsychological assessment battery, measures of cognitive task performance and everyday functioning) and fMRI data (i.e., task-related brain activity), analysed by training condition. In addition, exploratory analyses of individual differences in responsiveness to WMU training will be performed, by calculating correlations between amount of adaptive training task improvement and pre- to post-training change on neural, cognitive, and functional measurements.

4. Design and Methodology

i. Design

Randomised controlled trial methodology; specifically stratified randomisation in conjunction with permuted block random allocation, using an active control group will compare two conditions: (1) GMT combined with adaptive training [AT]; (2) GMT combined with non-adaptive [NA] training. Thirty-two adults with non-progressive ABI sustained in adulthood will be recruited from the NHS.. Participants will complete a combination of standard GMT (9 sessions) and 8 WMU (AT or NA) training sessions, delivered in small groups. Neuropsychological and functional assessments will be performed before and after the intervention. In addition, fMRI scanning sessions will be conducted pre- and post-training at the Clinical Research Imaging Facility (CRIF), Queen Elizabeth University Hospital (QEUEH) in a 3T Prisma Siemens scanner.

ii. Participants

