At both T1 and T2 the task runs will be followed by a T1-weighted sequence to obtain high-resolution anatomical images. In conducting fMRI data analysis the functional images will be spatially realigned using a six-parameter rigid body transformation and coregistered to their T1-weighted anatomical image. In total, visits 2 and 11 will take around two hours to complete, i.e. thirty minutes for the safety procedure prior to the scan and another one hour and a half for the scanning procedure itself. Comparisons in scanned task performance between T1 and T2 will allow us to examine how much benefit is gained due to the training intervention and if there is evidence of generalisation to other untrained tasks. In addition, we will examine neural changes in terms of task-related brain activity.

The procedure and tasks will be identical at T1 and T2, with the exception of three structural imaging sequences acquired only at T1, in addition to the T1-weighted anatomical image, for the purposes of a comprehensive, accurate and detailed neuroradiologist report (please see sections 6 and 7 below). These additional sequences are: 1. Axial T2-weighted, 2. Axial T2-weighted fluid attenuation recovery (FLAIR), and 3. A haemosiderin sensitive sequence.

For both fMRI sessions, the participants will spend no more than one hour inside the scanner.

Visits 3- 10: GMT+WMU Intervention sessions

There will be 8 weeks of a combined GMT and WMU intervention. Each GMT session will be two hours long while the WMU session will last between one hour and one hour and fifteen minutes. There will be a break between the training sessions allowing participants to have a rest and relax lasting between thirty minutes to an hour. The intervention visits will be conducted either at the Psychology department, University of Glasgow or at the CTCBI. Both GMT and WMU sessions will be administered by the PhD researcher undertaking the project. These will be conducted weekly on a group level at the same day; that means each intervention visit will last approximately three hours and forty-five minutes to four hours including the break in between. If attending both intervention sessions at the same day is not feasible for some participants, due to reasons such as getting easily fatigued or not being able to commit this long on the same day, the following guidelines will be implemented:

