Quantitative behavioural data will be analysed using SPSS 21 software or equivalent. Data on recruitment, adherence and retention rates will be summarised as percentages with 95% confidence interval (CI). Baseline characteristics of the sample will be presented using descriptive statistics. Measures of cognition (overall and domain specific composite scores) and psychological and functional constructs will be summarised by group and overall with 95% CI, and analysed using correlational analyses and t-tests or their non-parametric equivalents to estimate effect sizes (ES). The estimated ES, Cohen's d (Sullivan & Feinn, 2012), will be calculated using linear regressing adjusted for baseline and factors. The sample means, SD and change scores on these outcome measures will form the basis of sample size calculations for a further full-scale study, if indicated.

fMRI BOLD responses will be analysed using the general linear model implemented in SPM12 developed at the Wellcome Center for Human Neuroimaging, UCL (www.fil.ion.ucl.ac.uk/spm). Data preprocessing will include each participant's functional images being realigned using a six-parameter rigid body transformation and coregistered to their anatomical image. Covariates of interest will be constructed by convolving vectors of predicted neural activity with a canonical hemodynamic response function. To account for residual variance because of head movement, motion parameters will be estimated at the realignment stage of pre-processing and motion spikes will be identified using the ArtRepair toolbox (cbsr.stanford.edu/tools/human-brain-project/artrepair-software.html) and included in each model as covariates of no interest. For group analysis, functional images will be normalised to MNI (Montreal Neurological Institute) space using affine and nonlinear transformations, and spatially smoothed.

5. Data Storage & Sharing

All sensitive information such as participants' names, addresses, phone numbers etc will remain on NHS systems. All electronic anonymised data will be stored on secure University

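### The scanner-visit text credits T1–T2 change in scanned task performance to training, but the design identifies only adaptive versus non-adaptive difficulty, and Statistical methods does not carry that contrast through

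*Combined protocol and SAP*

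**What the plan says.** Section 4.x (Outline of Study Visits, Visits 2 and 11) describes three tasks done in the scanner before and after the intervention: Matrix Updating, the scanner version of a trained task; Spatial N-Back, for near transfer; and Object-Location Association, for far transfer. It then states "Comparisons in scanned task performance between T1 and T2 will allow us to examine how much benefit is gained due to the training intervention", and adds that the comparison will show any generalisation to untrained tasks. The sentence names no comparison between arms. The same section says "The procedure and tasks will be identical at T1 and T2", apart from extra structural sequences at T1.

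Other sections set out a randomised contrast:

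- Section 4.i (Design): the trial, "using an active control group will compare two conditions", gives GMT to both arms, with adaptive (AT) or non-adaptive (NA) working memory updating training. There is no untrained or GMT-only arm.
- Summary: "effect sizes of differences in pre- to post-training changes on neural, cognitive, and functional measurements will be determined by comparing two experimental groups".
- Section 3.ii (Secondary): change in behavioural data, including cognitive task performance, and in fMRI data is "analysed by training condition".
- Statistical methods: for measures of cognition and of psychological and functional constructs, Cohen's d "will be calculated using linear regressing adjusted for baseline and factors". Scanned task performance is not named. The fMRI paragraph covers preprocessing and the general linear model and gives no contrast between arms or of arm by time.

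**The concern.** A person who repeats a task some weeks later may do better because the task and the scanner are familiar, or because of other changes over the interval. Both arms are trained, so no group shows how large that gain is without training. A T1–T2 difference taken alone therefore cannot be credited to the intervention.

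This matters most for N-Back and Object-Location, because they carry the transfer question. As the sentence is worded, a retest gain on either could be reported as generalisation of training. Section 4.vii plans parallel test versions, where available, to limit practice effects in the neuropsychological battery; nothing similar is stated for the scanner tasks.

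The research question also leaves room for this reading. It asks about combining GMT "with an adaptive WMU training and how much benefit is gained", which could mean the benefit of the whole package or the increment from adaptive difficulty. The design can answer only the second.

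**Working it through.** **The plan's own figure.** The Sample size section gives 32 participants, 16 per group: 16 × 2 = 32, which agrees. The documents give no alpha, power, effect size, SD, practice gain or retest correlation for the scanned tasks, so there is no power calculation to reproduce.

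**What each comparison estimates.** Let B be the benefit of GMT plus non-adaptive training, D the extra effect of adaptive difficulty, and P the practice and time gain common to both arms. Expected T1–T2 change is:

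- NA arm: B + P
- AT arm: B + D + P
- pooled, equal arms: B + D/2 + P
- AT minus NA: D

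The arm difference removes P. Neither a within-arm nor a pooled change does, and nothing in the design estimates B apart from P.

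**Illustration of a within-person reading.** Assume B = D = 0, a practice gain g of 0.2, 0.3 or 0.5 baseline SD, equal SD at T1 and T2, a retest correlation r of 0.5 or 0.7, and a two-sided 5% paired t-test. All of these are assumptions.

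- Standardised change: dz = g / √(2(1 − r)). At r = 0.5 this equals g; at r = 0.7 it is g / 0.775.
- Noncentrality: dz × √n, with n − 1 degrees of freedom.
- Example: g = 0.2, r = 0.7, n = 32 gives dz = 0.258, noncentrality 0.258 × 5.657 = 1.46, critical t = 2.04, and a rejection probability of 0.29.

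| n tested | r | g = 0.2 | g = 0.3 | g = 0.5 |
|---|---|---|---|---|
| 32 (pooled) | 0.5 | 20% | 38% | 78% |
| 32 (pooled) | 0.7 | 29% | 57% | 94% |
| 16 (one arm) | 0.5 | 12% | 20% | 47% |
| 16 (one arm) | 0.7 | 16% | 31% | 68% |

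The two values of r differ only in how g converts to SD-of-change units.

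**The arm contrast under the same null.** In 40,000 simulated trials for each of g = 0.2, 0.3 and 0.5 (SD-of-change units, 16 per arm), the t-test of change between arms rejected 5.0%, 5.0% and 5.2% of the time. The mean difference was within 0.002 of zero throughout.

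**Precision of that contrast.** The unadjusted 95% CI half-width in SD units is t × √(2/n per arm). At 16 per arm it is 2.042 × 0.354 = 0.72. Section 4.ii and the COVID-19 plan in section 4.xi let some participants take part without scans, so fewer may contribute. If 12 or 10 per arm were scanned (an assumption), the half-width would be 0.85 or 0.94.

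**The case against.** A reader might infer that the plan as a whole counts practice and time as treatment benefit. The documents do not support that. The Summary and section 3.ii commit to comparing change between randomised arms, for cognitive task performance as well as fMRI data, and that comparison cancels any practice effect the arms share. The sentence at issue sits in a visit outline. It names no test, threshold or pooling, and it does not rule out the arm comparison: T1–T2 change is the quantity that section 3.ii then analyses by arm.

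A reader might also take the percentages above as the trial's false-positive rate. They are not. The plan specifies no paired test that declares benefit on scanned tasks, the gain and correlation are assumed, and 32 is the most that could be scanned. Nor does the statement that the tasks are identical show that the same stimuli or trial orders recur. It is there to set off the structural sequences acquired only at T1, and it says nothing about the size of a retest gain.

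All of that stands, and it reduces the point to a local one. It does not remove it. The general commitment does not withdraw the specific attribution. The arm comparison answers a different question from the benefit of training as a whole. Statistical methods, where an analyst would look, does not settle which reading applies to scanned performance or BOLD change.

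**Conclusion.** The point holds in a limited form. The scanner-visit section attributes within-person change on repeated tasks to training and to transfer, and this design cannot support that. What randomisation identifies is adaptive against non-adaptive difficulty. The plan already commits to that contrast in general terms but does not write it into Statistical methods for scanned performance and task-related activity.

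The documents do not fix a size. Under the stated assumptions, a pooled within-person test would mislead in about 20% to 94% of trials with no training effect, against about 5% for the arm contrast. The latter figure assumes that practice and time effects are the same in both arms.

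Severity is minor. The primary outcomes are feasibility, acceptability and fidelity, transfer is secondary, and the Sample size section says the study is not powered for group differences.

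**What to change.** In section 4.x, Visits 2 and 11, replace the sentence with: *The effect of adaptive difficulty on scanned task performance, including the near- and far-transfer tasks, is the AT–NA difference at T2 adjusted for T1 and aetiology stratum; within-arm T1–T2 change is descriptive and includes practice and time effects.*

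In Statistical methods, name scanned task performance among the outcomes of the baseline-adjusted regression, and add the matching AT–NA (group-by-time) contrast for BOLD change on each scanned task. Report each estimate with its confidence interval and the number scanned per arm.

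The cost is wording plus one regression per task and the corresponding group-level fMRI contrast, all from data already planned. No visits, participants or change in sample size are needed. The edit does not make the total benefit of GMT plus working memory training estimable; that would need an arm this trial does not have, so the report should not claim it.

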The following neuropsychological tests will be used:

1. Trail Making Test (TMT) A and B (Reitan, & Wolfson, 1985) to get an estimate of attention, speed and mental flexibility (~5min).
2. Hotel task (Manly et. al., 2002) to measure executive function in daily life activities (~20min).
3. Digit Span taken from the Wechsler Adult Intelligence Scale (4th edition), (Wechsler, 2008), to assess verbal memory (~7-10min).
4. Tower test, taken from the Delis Kaplan Executive Function System battery (D-KEFS) (Delis et al., 2001) to obtain scores in a task requiring planning, rule learning and inhibition (~20min).
5. Colour Word Interference (CWI) test from the D-KEFS battery (Delis et al., 2001), assessing inhibition of an overlearned response and flexibility (~10min).
6. Functional measurements will be obtained using the Dysexecutive Questionnaire (DEX) (Burgess et al., 1996) (~5min).

These neuropsychological tests have been carefully reviewed and selected as they have been previously used for assessing individuals with ABI in the following studies examining changes after a cognitive intervention: 1. TMT (Sohlberg et al., 2000; Novakovic Agopian et al., 2011;), 2. Hotel task (Manly et al., 2002; Levine et al., 2011; Tornas et al., 2016), 3. Digit Span (Westerberg et al., 2007; Miotto et al., 2009; Vogt et al., 2009), 4. Tower test (Levine et al., 2001; Tornas et al., 2016), 5. CWI test (Lundqvist et al., 2010; Novakovic Agopian et al., 2011;) and 6. DEX (Miotto et al., 2009; Spikman et al., 2010).

These assessments are essential in characterising the participant sample in terms of cognitive function and capturing changes resulting from the cognitive intervention. Information about participant's current medications and ABI rehabilitation will also be

collected. The PhD researcher will also write to the participants' GP to let them know that they are taking part in the study.

Following all baseline neuropsychological assessments, participants will be randomly allocated to either (1) GMT combined with adaptive WMU training [AT]; (2) GMT combined with non-adaptive [NA] WMU training. The two groups will be stratified by the following factor: aetiology of brain injury (two strata, i.e. traumatic brain injury (TBI) or stroke).

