1. The option of coming for the two interventions separately within the same week will be offered, i.e. arranging the GMT and WMU interventions at two different times.
2. The option of conducting the WMU intervention in one's own time at home will be offered after the PhD researcher makes sure the necessary requirements are in place, i.e. the participant has a laptop at home to perform the training tasks, they have fully understood the tasks and are practicing according to the guidelines. Under these conditions, task performance will be monitored from encrypted anonymised data files (logging trial accuracy and response time) transmitted to the PhD researcher via e-mail at the end of each at-home training session.

Visit 12: T3, Immediate follow-up: neuropsychological and functional assessments

All standardised measures that were administered at baseline (Visit 1) will be re-administered after the end of the intervention (please see table 1) by the PhD researcher. An acceptable period between the end of the intervention and neuropsychology assessment will be within three weeks. In addition, a feedback form will be given to the participants to rate the perceived usefulness and experience of the interventions. This final visit will last around one and a half hours.

The PhD researcher will have access to supervision and will be given advice regarding what steps to take, including sharing relevant information, if they become concerned about the welfare of the participant at any stage during the study.

xi. *COVID-19 mitigation plan- Online option for study visits 1, 3-10 and 12.*

An online alternative will be offered to run the study visits remotely in order to minimise the risk of infection due to COVID-19. As a result, no unnecessary travelling nor physical group sessions will be taking place. In more detail:

- *Neuropsychology assessment - Visits 1 and 12*

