The assessments listed in section 4vii will be adapted to be conducted remotely through an NHS approved software. Those tests that cannot be adapted for online use will be discarded and no further assessments will be used in their place, or, where feasible, these assessments may be adapted for delivery with social distancing when people come to CRIF for the scanning sessions, i.e. visits 2 and 11. After each participant, the test materials will be disinfected for use with the next individual. Another alternative is the use of a validated software via a secure web-based, GDPR compliant platform such as CANTAB, which is

designed and validated by Cambridge Cognition: <https://www.cambridgecognition.com/cantab>.

GMT- Visits 3-10

The GMT sessions will be conducted remotely via NHS IT systems to ensure security and data protection and the PhD researcher will use an NHS approved software (please see further information below). The session duration will remain the same while more regular breaks will be introduced. The PhD researcher will provide practice sessions, so participants familiarise themselves and feel comfortable using the software prior to starting the intervention. These will be part of visit 1 or any other time that is suitable for participants. The material, content and duration of the GMT will remain unchanged as described earlier. The PhD researcher will additionally record a brief five-minute video providing: 1. a recap for each session, 2. a brief summary of the key concepts explored and 3. a reminder of the homework for the next session. The video recording will be provided at the end of each GMT session only to those participants that were in attendance.

- WMU Training - Visits 3-10

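### Does the COVID-19 plan need a fixed delivery route and a same-mode rule for each neuropsychological test?

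*Combined protocol and SAP*

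**What the plan says.** Section 4.xi opens with the remote route as an offer: "An online alternative will be offered to run the study visits remotely in order to minimise the risk of infection due to COVID-19". For the battery it is firmer: "The assessments listed in section 4vii will be adapted to be conducted remotely through an NHS approved software". It then gives three ways out:

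- Dropping the test: "Those tests that cannot be adapted for online use will be discarded and no further assessments will be used in their place".
- Where feasible, in-person testing at the scans: "these assessments may be adapted for delivery with social distancing when people come to CRIF for the scanning sessions, i.e. visits 2 and 11".
- A web platform: "Another alternative is the use of a validated software via a secure web-based, GDPR compliant platform such as CANTAB".

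Three other provisions bear on the point. Under Visit 12, section 4.x says "All standardised measures that were administered at baseline (Visit 1) will be re-administered after the end of the intervention", and adds "An acceptable period between the end of the intervention and neuropsychology assessment will be within three weeks". On allocation, section 4.vii says "Following all baseline neuropsychological assessments, participants will be randomly allocated to either" one of the two arms. Sections 4.ii and 4.xi admit some participants who will not be scanned.

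The primary outcomes (section 3) are feasibility, acceptability and fidelity; the battery is secondary. The Sample size section states that the study is not powered to compare the arms, but it lists the variance of the outcome measures among the quantities to be estimated. The Statistical methods section intends to size a full trial from the means, SDs and change scores.

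**The concern.** Four routes are listed with no rule for choosing among them. The protocol does not say which tests cannot be adapted, or whether the choice is made per test, per participant or for the whole study. The requirement to repeat the same measures is silent on mode. A participant could therefore be tested in person at baseline and remotely at follow-up, and the mode effect would enter the change score. No mode field is mentioned, so the mixture might not be separable afterwards.

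Moving a test to the scan visits seems to raise two further problems. Unscanned participants have no Visit 2 or 11, and a baseline test at Visit 2 delays the earliest possible randomisation. Such a baseline would also follow the first GMT module, as the first scan already does.

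At stake are the SDs and change scores carried into a later trial. The Timeline section adds some weight: data collection continues for a year after the PhD project, so an unwritten convention would have to last that long.

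**Working it through.** The sample size of 32 has no alpha, power, effect size or SD behind it. It can be checked only as 2 × 16 = 32. The rest is a comparison of the text, with some arithmetic for scale.

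**Randomisation.** In Table 1, Visit 2 is at most 1 week after Visit 1, and Visit 3 at most 1 week after Visit 2.

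- All tests at Visit 1: time to randomise before Visit 3 is at most 1 + 1 = 2 weeks.
- A test at Visit 2: at most 1 week.

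No section places allocation before Visit 2. The first GMT module is individual and the same for both arms, so allocation is first needed at Visit 3, when the working-memory training starts. The rule in section 4.vii already covers a baseline that ends at Visit 2.

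**Unscanned participants.** Scan-visit testing is conditional on feasibility. Someone with no scan visit can fall under the discard option or the web platform. The ordinary test settings in section 4.vii (the treatment centre or the university) are not withdrawn either. The consequence is a smaller n for that test: each unscanned participant removes 1/32 = 3.1%. If, as an assumption, 12 or 8 per arm remained instead of 16, the 95% half-width for d near zero, 1.96 × √(2/n), would be:

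| n per arm | half-width |
|---|---|
| 16 | 0.69 |
| 12 | 0.80 |
| 8 | 0.98 |

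The loss is visible in the reported n and interval.

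**Mode before and after.** From Visit 1 to Visit 12, Table 1 gives at most 1 + 1 + 7 + 1 = 10 weeks, or 1 + 1 + 7 + 3 = 12 with the three-week allowance. Circumstances could change in that time. Two forms of mixing are already limited by the text: a web-platform test substituted for an original is a different measure, so pairing the two would depart from the Visit 12 rule; and Visits 2 and 11 are both in person. What remains is the same test given remotely once and face to face once, or by different routes in different participants.

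**Possible size.** The documents give no mode effect and no switching rate. Assume a shift of 0.2 to 0.5 SD of the change score, always in the same direction, in 25% to 50% of participants.

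- Bias in mean change = shift × share: 0.2 × 0.25 = 0.05 to 0.5 × 0.50 = 0.25 SD.
- Bias between arms, if 4 more of 16 switch in one arm: 0.2 × 4/16 = 0.05 to 0.5 × 4/16 = 0.125 SD, against a half-width of 0.69.
- SD of change, worst case, with switching unrelated to true change: √(1 + 0.5² × 0.5 × 0.5) = √1.0625 = 1.03, a rise of 3%.
- Sampling error of a pooled SD: the upper 95% limit is √(df/χ²(0.025, df)) times the estimate. At n = 32 (df = 30) this is 1.34.

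**Share of the battery.** The listed times sum to 5 + 20 + 7 + 20 + 10 + 5 = 67 minutes, or 70 with the longer Digit Span. If, as an assumption, the Hotel and Tower tests were the ones moved or dropped, that is 40/70 = 57% to 40/67 = 60%. This shows how much of the battery could be affected; it does not measure bias.

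**The case for a change.** The best case for a change is that variance estimation is a stated purpose of the sample, so the lack of power for the arm comparison does not dispose of the matter. The protocol protects comparability elsewhere: parallel test forms are used where available, and the scanning tasks are the same on both occasions. Yet it says nothing on mode for the battery. The planned effect-size model does not name mode, and the overall and domain composites would have different components if tests were dropped or moved for some participants only. A list of tests by route and a mode field would cost little.

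Most of this is accurate. There is no written same-mode requirement, no criterion for the web platform and no stated plan to record mode. In the worst illustration, a bias of 0.25 SD in mean change would not be trivial.

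It still falls short of a reason to amend. The discard sentence reads naturally test by test for the whole study, which keeps the composites uniform. That the individual tester chooses, or that the assessor will change after the PhD project, is inference. Fixing one route per test for the whole study would remove flexibility that the COVID-19 section was written to provide. A sensitivity analysis by mode within 32 participants would be very imprecise.

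**Conclusion.** No change follows. The text is incomplete on delivery mode, but no rule as written produces a wrong result. Randomisation timing is already settled, and unscanned participants have a route or are simply absent from that test's n. The rule on repeating measures excludes the worst pairing.

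What remains is operational detail on secondary outcomes of a study not powered to compare the arms. A competent team would hold mode constant for each person where possible, note it on the test record, and report any scan-visit test with its own n.

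The size is unknown because the documents give neither a switching rate nor a mode effect. Under the assumed ranges, the effect on the SD (up to 3%) is small beside its sampling uncertainty (34% at the upper limit), and the between-arm bias (0.05 to 0.125 SD) is small beside a half-width of 0.69. The conclusion rests on mode being logged in practice and on switching being driven by pandemic conditions and not by arm. If mode went unrecorded and switching were common, the mean change within each arm would need cautious reading.
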